Study Design: A prospective pre/post intervention study with 10 ambulatory children with CP will compare their current AFO to the AFO-FC. Participants will be recruited from the Rehabilitation clinic and Physical Therapy patient caseloads of the investigators. Maximal knee extension in stance as well as gait speed (aim 1) will be captured by gait analysis at the Orthocare Innovations biomechanics laboratory in Mountlake Terrace. Community walking activity will be captured with the ankle-worn StepWatch accelerometer (aim 2). Mobility based participation in day to day life will be documented by parental report of the Assessment of Life Habits for Children (Life-H). Physical activity will be sampled with the Activity Scale for Kids – Performance (ASKp) and satisfaction with the respective devices will be examined with parental report of the Orthotic and Prosthetic Users' Survey (OPUS).

Two outpatient study visits will be carried out before (baseline) and after (follow-up) the standard of care clinical visits to cast/fabricate and fit the participants' new AFO-FC devices. At the baseline study visit, informed consent/assent, three dimensional gait analysis, parental report of mobility-based community participation, physical activity and satisfaction with device will be carried out while wearing their current orthoses. At the end of that visit, the participant will go home wearing the StepWatch accelerometer and GPS monitors for 2 weeks. The accelerometer will be returned to study staff by postage paid envelope. The child then has the appropriate clinical visits to cast, fabricate, fit and tune their new AFO-FC with a home walking program as appropriate. Consistency of clinical AFO-FC prescription will be addressed by the use of the published algorithm,¹ (Appendix) currently utilized clinically by the investigators here at Seattle Children's Hospital (SCH). All the AFO (plastic brace) portions of the AFO-FC devices will be casted at SCH and fabricated at Cascade DAFO (Dynamic Ankle Foot Orthoses), Inc.. The family of the participant will supply the footwear (shoes). The footwear portion of the AFO-FC will be modified, fitted and tuned along with the AFO portion by the SCH orthotists and [name]. Three months after the AFO-FC is tuned and finalized, they will return for the second study visit (follow-up) where all outcomes are collected again.

These results will provide the preliminary data essential for development and federal funding of a randomized clinical trial comparing current standard of practice "traditional" AFO to the AFO-FC approach. Study participation takes 12-16 weeks within clinical orthotic management.

Primary Objective: Examine the effect of AFO-FC on the primary outcomes of maximal knee extension during stance and gait speed as compared to current AFO prescription.

Secondary Objectives: Examine the effect of AFO-FC on daily walking activity, intensity and mobility-based participation and satisfaction as compared to current AFO prescription.

Sample Size: 10 children.

Study Duration: 12 months ending Sept 30, 2015.

Background and Significance

Cerebral palsy (CP) is the most common and costly neuromuscular condition among children in the US ^{2, 3}, with a prevalence of 3.3-3.8/1000 ⁴. The clinical definition of CP is a group of disorders of movement and postural development which result in physical activity limitations. ⁵ A novel and comprehensive strategy has been articulated in the AFO-FC approach¹¹, but neither the previous strategy (AFO type)¹² nor the new strategy (AFO-FC)¹¹ has strong published evidence of efficacy.(Fig 1)

[figure not shown]
As typically developing children walk, the lower extremity segments (femur, tibia and foot) align such that the knee extended (straight) during midstance. This allows support of body weight transfer during single limb support and swing through of the opposite leg while walking.(See Figure 2) During terminal stance when the heel is leaving the ground, the segments of the leg demonstrate a straight knee allowing an adequate step length and weight transfer as the opposite foot contacts the surface.¹³

In contrast, ambulatory children with CP present with crouch gait characterized by misalignment of the segments of the lower extremity (femur, tibia and foot). This misalignment of lower leg segments does not adequately support the transfer of weight with a resulting inefficient walking pattern.¹⁴ (Figures 3-5) During midstance when the foot should be flat on the surface, youth with CP present with either excessive or insufficient lower limb inclination (tibia) from vertical to support weight on one leg. For example crouch gait (Figure 3 & 4) is defined as excessive knee flexion in single limb stance. Excessive knee flexion during stance requires additional effort to walk,¹⁵ causing fatigue and reducing walking behavior in children with CP. It can be observed visually, but only computerized gait analysis has sufficient accuracy to inform clinical decisions. This heterogeneity of walking patterns in CP requires an individualized approach to orthotic prescription as well as motor training to optimize walking skills.¹³

Figure 1 AFO-FC.

Fig. 2. TYPICALLY DEVELOPING GAIT: MIDSTANCE TERMINAL STANCE

Common Gait Patterns: Spastic Diplegia

[figure not shown]

Fig 3. Abnormal leg segment alignment in CP

The current regional (Pacific Northwest) standard of care for orthotic prescription in ambulatory CP is usually an AFO that allows ankle movement (See Figure 4). This approach does not provide adequate alignment of the segments of the leg (knee is flexed) during midstance and terminal stance), which is due to insufficient control and weakness of the muscles about the ankle joint. A crouch gait walking pattern creates excessive demand on the knee extensors, results in shorter strides and an inefficient walking pattern. The habitual use of a crouch gait pattern significantly increases the energy cost of walking.¹⁶ In fact, a crouch gait pattern is associated with the need for future orthopedic surgery¹⁵ and an overall decrease in physical activity into adulthood.¹⁷ In contrast, the AFO-FC approach with individualized segment alignment and shoe modifications limits ankle movement and appears to enhance knee extension during mid and terminal stance. (See Figure 5)

[figure not shown]
[figure not shown]
As compared to typically developing children, youth with CP take significantly fewer steps per day and spend less time walking and engaging in activities of high intensity.¹⁸ van den Berg-Emans et al. reported that school children with spastic diplegic CP were less physically active than a healthy control group and that a typical child with CP would need to exercise 2.5 hr/day to reach the activity level of peers.¹⁹ Children with CP have also been described as having one of the most sedentary lifestyles among pediatric disabilities.²⁰ In a study of school-based activity performance and participation in Israel, youth with CP had significantly lower physical activity performance as measured by the School Function Assessment (SFA). The youth with CP participated significantly less often than their typically developing peers in daily school activities (i.e., playground games and moving to other areas of the school).²¹ Walking mobility has also been shown to be predictive of restrictive participation in mobility, education, and social relations for children with CP.²²

It is important to consider the implications of walking activity across the life span. In a California Developmental Disabilities Database study, Strauss, and colleagues (2004) reported the longitudinal functional skills of adults with CP at the ages of 20, 40 and 60 years. A marked decline in walking ability especially in late adulthood (age 60), was documented.²³ Self-reported functional walking in the community setting in late adulthood was associated with a longer life expectancy. CP leads to serious health problems that persist into adulthood^{2, 24}, and interventions to improve mobility are common although

Fig. 4. CEREBRAL PALSY-CROUCH GAIT AFO ALLOWING ANKLE MOVEMENT: MIDSTANCE TERMINAL STANCE

Fig 5. CEREBRAL PALSY-CROUCH GAIT AFO-FC - NO ANKLE MOVEMENT MIDSTANCE TERMINAL STANCE

only partially effective in altering the progression of the musculoskeletal consequences of the condition.

We have documented improvement in community walking activity with the StepWatch accelerometer in a clinical cohort of 8 children with bilateral CP comparing their current AFO with the AFO-FC approach.²⁵ The children represented the following gait patterns: 3 equinus, 4 crouch and 1 jump gait (See Figure 6). Current AFO prescriptions all allowed full or partial ankle movement except for one child with a solid ankle without individualized leg segment alignment or shoe modifications. Average strides per day increased for all participants wearing the AFO-FC with an average group increase of 2,611 strides/day and a range increase from 387 to 3020. A minimal clinical important difference (MCID) in daily walking activity of 2,478 stride/day has been calculated from 37 children with CP for the average difference in strides/day walking with an assistive device to without.²⁶ Thus, our clinical experience with the AFO-FC approach suggests positive influence on community walking activity.

Summary

The proposed protocol will help to substantiate our clinical experience with this novel approach to orthotic management in ambulatory children with CP. Currently there is no standardized approach for the orthotic management of this heterogenous population. Knowledge generated will lay the foundation for examining the proposed biomechanical mechanisms as well as translation to improved walking in day-to-day life. This work will document the effect of the AFO-FC approach on maximal knee extension in stance and walking speed (Aim 1). We hypothesize that improved knee extension in stance will produce increased walking activity in the community and parental report of mobility-based participation, physical activity and satisfaction with the devices. (Aim 2)

[figure not shown]

Fig .6 Average strides/day current AFO versus AFO-FC

Objectives

Primary Objective

- **Aim 1: Examine the effect of AFO-FC on the primary outcomes of maximal knee extension during stance and gait speed as compared to current AFO prescription.**
We hypothesize that 1) the ability to generate adequate knee extension in stance is impaired in their current AFO and contributes to limitations in gait speed and subsequent daily walking levels and intensity, and 2) the individualized leg segment alignment of the AFO-FC will produce positive improvements in knee extension during stance. Increased knee extension during stance will enhance the stability of stance phase, facilitate longer strides lengths and increased gait speed.
- Knee extension during stance and gait speed will be measured by computerized three dimensional gait analyses.
- Walking performance will be measured with the StepWatch accelerometer in each participant's daily environment (39).

Secondary Objectives

- **Aim 2: Examine the effect of AFO-FC on daily walking activity, intensity and mobility-based participation and satisfaction as compared to current AFO prescription.** We hypothesize that AFO-FC through improved knee extension during stance will result in faster walking speed facilitating a positive effect on community walking activity levels, intensity, mobility based day to day participation and satisfaction with device. Walking activity will be captured by the StepWatch accelerometer with participation and satisfaction assessed using parental report questionnaires
- Mobility based participation in day to day life will be documented by parental report of the Assessment of Life Habits for Children (Life-H).
- Physical activity will be sampled with the Activity Scale for Kids – Performance (ASKp)
- Satisfaction with the respective devices will be examined with parental report of the Orthotic and Prosthetic Users' Survey (OPUS).

Study Design and Methodology

We will conduct a prospective pre/post intervention study with 10 ambulatory children with unilateral (hemiplegia) or bilateral (diplegia) CP between the ages of 4 to 14 years. Participants will be recruited from the Rehabilitation clinic and Physical Therapy patient caseloads of the investigators. Two outpatient study visits will be carried out before (baseline) and after (follow-up) the standard of care clinical visits to cast/fabricate and fit the participants' new AFO-FC devices.

Outcomes —Maximal knee extension in stance as well as gait speed (aim 1) will be captured by 3 dimensional gait analysis at the Orthocare Innovations biomechanics laboratory in Mountlake Terrace. Community walking activity will be captured with the ankle-worn StepWatch accelerometer (aim2). Mobility based participation in day to day life will be documented by parental report of the Assessment of Life Habits for Children (Life-H). Physical activity will be sampled with the Activity Scale for Kids – Performance (ASKp) and satisfaction with the respective devices will be examined with parental report of the Orthotic and Prosthetic Users' Survey (OPUS).

Gait Analyses: Two gait analyses at self-selected walking speed will be conducted. At the baseline visit, gait will be recorded barefoot (to characterize gait pattern, Figure 3) and with current orthoses and shoes. Three months later, at Visit 2, gait analysis barefoot and with the AFO-FCs will be performed. To ensure consistency of motion data, markers will be attached by the same experienced lab personnel using the Plug In Gait model. Post-processing of all gait lab data will be carried out by one individual. Markers will be placed on the

[figure not shown]

Figure 7. Knee extension output from gait analysis

child to accurately collect the three dimensional joint motions and forces using an 8-camera Vicon MX system with two integrated AMTI force platforms. Primary outcome variable: Maximal knee extension in terminal stance will be extracted from the data to quantify crouch gait in the current AFO vs. the AFO-FC. (Figure 7) Additional joint motion and force data will also be reviewed to understand the interactions of possible gait adaptations displayed by the participants.

StepWatch (SW): Accelerometers will be used to determine how much participants actually walk on a daily basis. The StepWatch (SW) is a small, lightweight device that looks like a pager and is strapped around the ankle. The SW measures the number of steps taken during a day at low, medium and high intensities. Participants will take this device home and wear it during walking hours for two weeks. Participants will return the SW by mail using a stamped mailing envelope supplied to them. The walking activity in average number of steps per day as well as number of steps in each intensity level per day will be obtained. These variables will be averaged for a total week of activity, weekday activity, and weekend activity to be used in the analysis.

Activity Scale for Kids-Performance Version (ASKp): The ASKp, a child self-report questionnaire measures what the child "did do" during the previous week. It will be used to measure activity performance in this study. Validity, reliability and sensitivity of this measure have been established for the population in this study.²⁷ There are 7 sub-domains represented within the ASKp including: personal care (3 items), dressing (4 items), other skills (4 items), locomotion (7 items), play (2 items), standing skills (5 items), and transfers (5 items). Child report will be used. The 30 items aggregate will be used to obtain one overall summary score for analysis.

Assessment of Life Habits (Life-H): The LIFE-H questionnaire will be used to sample mobility-based life habits carried out in the participant's natural environment (home, school, neighborhood). For the purpose of this study the LIFE-H short form for children 5-13 years will be used, which, per developer is appropriate for 4 year-olds as well. The domains of housing, mobility and recreation will be the focus of this study. The LIFE-H produces a continuous score ranging from 0 to 9, which are developed by combining the results of the sub-score related to the degree of difficulty and type of assistance. The instrument also has a separate satisfaction scale that provides the individual's assessment regarding accomplishment of life habits (5-point Likert scale). Parental report will be used in this study. The mean of each category (mean of items) for accomplishment and satisfaction will be used in the analysis.

Orthotic and Prosthetic Users' Survey (OPUS): The OPUS is a self-report instrument that was developed to assess patient outcome in the areas of functional status, quality of life, and satisfaction with devices and services.²⁸ For the purpose of this study only the satisfaction with device scale will be used. It consists of 11 questions addressing orthotic comfort, fit, and wearability and uses one rating scale with four "extent of agreement" response categories. Child report will be used as feasible and if not then parental report will be collected. Data will be converted to ordinal or nominal data categories for analysis.

Study Population

Sample Size

Our long-range plans are to carry out a multi-site randomized trial comparing AFO-FC with AFO. Feedback from the NIH regarding these plans has indicated that we should first collect preliminary data on effect sizes and variability, in order to inform sample size and power calculations for such a study. Our TRIPP proposal is designed to achieve this goal within the time and budget limitations. Therefore, the proposed study is neither designed nor powered for inference on the intervention's efficacy. Sample size of 10 is proposed logically feasible given the 12 months of funding and clinical caseloads of the investigators. This data will be used to

calculate effect size and standard-deviation estimates for the endpoints described above. These estimates will be reported together with graphical and table summaries of the raw data, as relevant.”

Inclusion /Exclusion Criteria

Inclusion Criteria

1. Male or female, ages 4 to 14 years old, inclusive.
2. Has a diagnosis of cerebral palsy, of a diplegic, unilateral or bilateral distribution
3. Uses walking as primary method of mobility at school, home, and the community, and has a GMFCS level of 1, 2 or 3.
4. Barefoot gait pattern demonstrating leg segment misalignment consistent with the patterns in Figure 3.
5. Family has resources to attend all study sessions (i.e. transportation/schedule).
6. Currently wearing orthoses or clinically appropriate to wear orthoses to enhance walking activity.
7. Clinically deemed appropriate for a trial of the AFO-FC approach by the investigators

Exclusion Criteria

1. Non – English speaking.
2. Foster children or wards of the state.
3. Uses wheelchair or stroller mobility as a primary method of mobility, and uses walking either only at home, or only in therapy sessions.
4. Severe visual impairment, such that the visual impairment itself functionally limits mobility.
5. Any Orthopedic or Neurosurgery surgeries in the last 3 months.
6. Any Phenol or Botox injections to the legs in the last 3 months.
7. Uncontrolled seizure disorder, as defined as any seizure in the last 3 months which impacted their mobility skills and function. Seizures which did not affect their mobility are acceptable.
8. Unable to understand directions sufficiently to complete the study assessments.
9. Lower extremity fracture in the last 3 months.
10. Planned surgery or changes to medication during the study period.

Restrictions during the study:

1. Any medications which affect muscle tone or movement disorders are at a stable dose for 30 days prior to Baseline, and agree to maintain a stable dose during the protocol. If a dose change is needed, this will be recorded, and the child will stay on the study if the family still wishes to participate.
2. Participants' current physical therapy program will be continued throughout the protocol.

Study Duration and Timeline

Study Task	Study Period Months				
	1	2-9	10	11	12
IRB					
Train Intervention/Assessment staff					
Recruitment/Enrollment					
Assessment/Intervention					
Post Treatment Follow up Assessments					
Data Analysis and Manuscript preparation					

The project will begin Oct 30, 2014 and end Sept 30, 2015 per published call for submission guidelines

Study Visits and Procedures

	Baseline Visit	Post Treatment Visit
Study Week	Occurs after 1) Deemed clinically appropriate for AFO-FC 2) Family expresses interest in participation 3) Prior to fitting of new AFO-FC prescription appointment	3 months post clinical fitting of new AFO-FC prescription appointment (+/- 2 weeks)
Visit Number	1	2
Informed Consent	X	
Demographics	X	
Medical and Surgical History	X	
Gait Lab Assessment – Orthocare Innovations Biomechanics Lab	X (Barefoot & with current AFO prescription/shoes)	X (Barefoot & with AFO-FC)
Height	X	
GMFCS	X	
CFCS	X	
MACS	X	
ASKp	X	X
Life-H	X	X
OPUS	X	X
Concomitant Medications	X	X
Adverse Events		X
StepWatch Calibration/ Monitoring	X	X
GPS Monitoring	X	X

*ASKp is given to family to take home and complete on the day their monitors are returned.

Recruitment and Pre – Screening

Participants will be approached regarding interest in the study, once deemed clinically appropriate for the AFO-FC prescription by Drs. [name] and [name]. The investigators (Drs. [name] and [name]) will ask family if they are interested in hearing about the study. They will then be contacted by the study CRA or [name] to describe the study and answer questions. [name] will coordinate and schedule baseline visit.

Baseline Visit

A Baseline visit will be scheduled after 1) deemed clinically appropriate for the AFO-FC prescription, 2) family expresses desire to participate and 3) before the final fitting of the new AFO-FC prescription.

- Informed consent and assent and HIPAA authorization
- Demographic and medical history questionnaire, include current medications, prior surgeries, and outside physical therapy. Questionnaire includes maternal level of education, whether the family owns or rents their home, type of orthotics used, and contact information for any community therapist caring for the child.
- Gross Motor Classification System (GMFCS) scoring
- Communication Function Classification system (CFCS) scoring
- Manual Ability Classification system (MACS) scoring
- Gait Lab Assessment – Orthocare Innovations Biomechanics Lab-barefoot & with current AFO/shoe prescription.
- LIFE – H survey (completed by parent during visit)
- OPUS Survey (completed by parent during visit)
- Activity Scale for Kids (ASKp) (sent home for parent to complete at end of wearing of monitors)
- StepWatch: Calibration and fitting of the StepWatch activity monitor in a knit cuff on the left ankle. Children will be instructed to wear the StepWatch for the next 7 days while awake and not in the water, and to return it at their first treadmill training program session. Parents will be instructed to complete the ASKP on the 7th day of wearing the monitor and return by postage paid envelope..
- GPS: Children will be instructed in the use of the Global Positioning System (GPS) monitor at this visit with the same wearing and return protocol as the StepWatch. This device will be worn in a knit cuff on the right ankle.

Clinical Intervention

The child then has the appropriate clinical visits to cast, fabricate, fit and tune their new AFO-FC with a home walking program as appropriate. Consistency of clinical AFO-FC prescription will be addressed by the use of the published algorithm,¹ (Appendix) currently utilized clinically by the investigators here at Seattle Children's Hospital (SCH). All AFO portions of the AFO-FC devices will be casted at SCH and fabricated at Cascade DAFO (Dynamic Ankle Foot Orthoses), Inc., Ferndale WA. Families supply the shoes or footwear. The combined AFO with the footwear combinations FC will be fitted and tuned by the SCH orthotists and [name] consistent with the published algorithm.

Post Treatment Visit

The single follow up visit will be conducted 3 months post clinical fitting of new AFO-FC prescription appointment (+/- 2 weeks).

- Record any adverse events, and update the concomitant medications and concomitant therapy form.
- Gait Lab Assessment – Orthocare Innovations Biomechanics Laboratory-barefoot & with AFO-FC prescription.
- LIFE – H survey (completed by parent during visit)
- OPUS Survey (completed by parent during visit)
- Activity Scale for Kids (ASKp) (sent home for parent to complete at end of wearing of monitors)
- StepWatch: Calibration and fitting of the StepWatch activity monitor in a knit cuff on the left ankle. Children will be instructed to wear the StepWatch for the next 7 days while awake and not in the water, and to return it at their first treadmill training program session. Parents will be instructed to complete the ASKP on the 7th day of wearing the monitor, and return by postage paid envelope.
- GPS: Children will be instructed in the use of the Global Positioning System (GPS) monitor at this visit with the same wearing and return protocol as the StepWatch. This device will be worn in a knit cuff on the right ankle.

Statistical Analysis Plan (See sample size above)

The primary analysis for both aims will be descriptive for direction of effect and to generate effect size and power analysis for future multi-center R01 grants.

Informed Consent Process

The child's parent/legal guardian will be approached for informed consent at the baseline visit. The study staff will review the consent form with the parent to explain study procedures, study purpose, voluntary nature of the study, and possible risks and/or benefits to the child and guardian. If the child is 7 years old or older and thinks and makes decisions at least as well as a 7 year old, then the child will complete an informed assent process with the study staff. This may include drawing pictures, verbal explanations, reading portions of the assent form out loud, and other methods, to ensure that the child understands the study purpose, procedures, and voluntary nature of the study. If the child agrees, he/she will sign an assent form, and have the researcher co-sign as indicated. Non – English speaking children will not be eligible, as there is not adequate interpreter support at the study locations. In addition, the activity surveys have not been validated in other languages.

Privacy and Confidentiality

Study data will be recorded on case report forms without any identifiers, coded with a study code, and stored in locked drawers in secure offices at Seattle Children's Research Institute. Study data will also be stored electronically in secure computer files and drives at Seattle Children's Research Institute and through REDCap at SCRI accessible only by study staff. Gait lab data containing only the study ID will be stored electronically in secure computer files and drives at Orthocare Innovations. Anthropometric data collected as part of the gait analysis will be stored in locked file cabinets, by study ID.

Risk/Benefit

Risk to participants

Falling: There is a less likely, mild risk of falling during gait study assessments and treadmill training. All walking tests will be conducted on indoor, on non-skid surfaces designed for gait analysis, to reduce the risk of injury resulting from falls.

Muscle soreness and fatigue: There is a likely, mild risk of muscle soreness, and fatigue resulting from the exertion involved in the walk tests.

Skin irritation: There is a rare, mild risk of skin irritation due to wearing the StepWatch monitor on the left leg and the GPS on the right ankle. These monitors are worn with soft knit cuffs, similar to a sock, thus risk of irritation if rare. Families will be instructed to check the skin for any problems periodically, and to take a break if needed.

Emotional distress or embarrassment: There is a rare, mild, risk of emotional distress or embarrassment due to completing the research surveys. Parents will be informed that they can take a break or skip questions if they need to.

Loss of privacy: We were concerned about the possible loss of privacy for children who complete the GPS monitoring. To prevent this, all GPS data will be analyzed together, after the last child has completed study participation. The GPS maps will not be available to children or their parents.

Benefits to participants

Participants will likely benefit from information collected within the study protocol (gait lab, walking activity and parent surveys). This information has potential to inform the clinical orthotic management of the participant.

Data Safety Monitoring

The principal investigator will review any adverse events as they occur, and will report any possibly or definitely related adverse events to the IRB in accordance with their policies.

Conflict of Interest

None

Publication and Presentation

Results from this pilot study will be presented at appropriate professional conferences and submitted to appropriate journals.

Data and/or Sample Sharing

Data will not be shared with parties outside of the research team.

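### The only scheduled adverse-event entry is at Visit 2, so the take-home monitor period that starts there, and delayed soreness after the second gait session, have no scheduled enquiry

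*Protocol*

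**What the plan says.** - **Schedule table (Protocol, Study Visits and Procedures).** The row "Adverse Events" is marked under the Post Treatment Visit only. The baseline cell is blank.
- **Visit lists.** The Baseline Visit list has no adverse-event item. The Post Treatment Visit list has one: "Record any adverse events, and update the concomitant medications and concomitant therapy form".
- **Timing.** "The single follow up visit will be conducted 3 months post clinical fitting of new AFO-FC prescription appointment (+/- 2 weeks"). Baseline takes place "before the final fitting of the new AFO-FC prescription", with no minimum or maximum interval given.
- **Exposures.** Both visits include a gait session, and after both the child goes home with a StepWatch and a GPS monitor. The visit lists give 7 days of wear; the Study Design summary and the StepWatch outcome paragraph give two weeks.
- **Risk to participants.** "There is a likely, mild risk of muscle soreness, and fatigue resulting from the exertion involved in the walk tests". There is also a "rare, mild risk of skin irritation due to wearing the StepWatch monitor on the left leg and the GPS on the right ankle". Families are told to look at the skin and pause wear if there is a problem. This section does not ask them to tell the study.
- **Data Safety Monitoring.** "The principal investigator will review any adverse events as they occur", and possibly or definitely related events go to the IRB. No collection route and no end date are stated.
- **Take-home form (schedule footnote).** "ASKp is given to family to take home and complete on the day their monitors are returned".
- **SAP.** It describes a different, randomised waitlist design and has no text on adverse-event collection.

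**The concern.** The delayed risks that the protocol names arise twice per child: after the baseline visit and after Visit 2. The schedule asks about adverse events once, at Visit 2. Whatever develops in the days after Visit 2, when the monitors are worn again and soreness from the second gait session would appear, has no scheduled enquiry. What happened in the days after baseline is asked about only at the far end of the study.

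At stake is the completeness of a small safety record. If staff follow the schedule as written, solicited reports of monitor irritation and walk-test soreness will cover one of the two exposures, and that one after a long delay. The investigator's ongoing review then depends on families volunteering mild problems without being asked.

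**Working it through.** No sample size, power or error rate is involved, and the plan states no figure of its own to reproduce. The check places exposures against the one scheduled entry and then does calendar arithmetic.

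**1. Exposure against enquiry**

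| Named delayed risk | Arising after baseline | Arising after Visit 2 |
|---|---|---|
| Soreness and fatigue from walk tests | Asked about at Visit 2 | No scheduled enquiry |
| Skin irritation from monitors | Asked about at Visit 2 | No scheduled enquiry |

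The right-hand column does not depend on when during Visit 2 the question is asked. Any moment within that visit precedes the second take-home period and next-day soreness.

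**2. Share of exposure after the only entry**

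Monitor-days = children × periods × days per period. Inputs: 10 children (Sample Size), two periods (schedule), 7 or 14 days (the two stated wear lengths).

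- 7 days: 10 × 2 × 7 = 140 in total; after Visit 2, 10 × 1 × 7 = 70; 70/140 = 50%.
- 14 days: 10 × 2 × 14 = 280 in total; after Visit 2, 10 × 1 × 14 = 140; 140/280 = 50%.
- Gait sessions: 10 × 2 = 20 in total, of which 10 are at Visit 2.

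The 50% holds at either wear length, provided the two periods are equally long. These are counts of exposure, not of expected events. The documents give no event rates.

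**3. Delay before baseline-period events are asked about**

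Three months = 365.25/12 × 3/7 = 13.0 weeks. Visit 2 is therefore 13.0 ± 2 = 11.0 to 15.0 weeks after fitting. Let g be the time in weeks from baseline to fitting. The documents do not state g, so it is varied as an assumption. Baseline to Visit 2 = g + (11.0 to 15.0):

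- g = 0 (fitting directly after baseline): 11.0 to 15.0 weeks.
- g = 1 (7-day wear completed first): 12.0 to 16.0 weeks.
- g = 2 (14-day wear completed first): 13.0 to 17.0 weeks.
- Four further weeks for casting and fabrication: 16.0 to 20.0 weeks (7-day wear) or 17.0 to 21.0 weeks (14-day wear).

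If the first wear period ends before fitting, the gap from its end to Visit 2 is at least 11.0 weeks. As a cross-check, the protocol puts participation at 12 to 16 weeks. If that includes the second wear period, baseline to Visit 2 is between 12 − 2 = 10 and 16 − 1 = 15 weeks. The 10-week end cannot be met, because Visit 2 is at least 11 weeks after fitting and baseline precedes fitting.

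**4. Can the take-home form carry the question?**

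The footnote ties ASKp completion to the day the monitors are returned; the visit lists tie it to the seventh day of wear. At 7 days' wear these can coincide. At 14 days' wear, a form completed on day 7 would miss 14 − 7 = 7 of the 14 days.

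**The case against.** The strongest reply is that the one-time entry is not the whole system. The Data Safety Monitoring section commits the principal investigator to ongoing review, with no cut-off at Visit 2. The natural reading is spontaneous reporting throughout plus one scheduled enquiry. Participants come from the investigators' own caseloads and attend casting, fitting and tuning visits between the study visits. The consent form, which is not among the documents available here, may tell families whom to contact.

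Much of this stands. A reader might infer from the schedule that irritation or soreness after Visit 2 cannot be captured at all; the documents do not support that, because a family can report unprompted. What remains is that ongoing review is a commitment to act on events, and the schedule gives no step that brings events in. The clinical visits list no adverse-event enquiry and fall before Visit 2. Monitor return does not fill the gap either: one section has the StepWatch posted back, and the visit lists have it handed in at a treadmill session that the schedule does not contain.

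Four other stronger readings also fail:

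- That adverse events are recorded at the start of Visit 2. This rests only on the order of a bullet list that is not said to be chronological.
- That recall of baseline events is always three months or more. The visit window allows about 11 weeks.
- That falls in the gait laboratory depend on recall. Staff would witness them.
- That a skin-related break in monitor wear biases the walking outcome. Nothing in the documents demonstrates this, and StepWatch data are obtained by day, so a full day off might be visible.

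Proportion matters too. The protocol rates soreness as mild and skin irritation as rare and mild, the study is a descriptive 10-child pilot with no safety objective, and the single entry comes after about three months of AFO-FC wear, so the intervention period up to Visit 2 is covered.

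**Conclusion.** The point holds as a minor gap in solicited collection. The only scheduled entry is at Visit 2. Half of the planned monitor-days and the aftermath of 10 of the 20 gait sessions follow it with no scheduled enquiry, although the protocol names a risk for each. Skin or soreness events after baseline that are not volunteered would be asked about only about 11 weeks or more later. Ongoing review by the principal investigator is stated, but no scheduled collection step supports it.

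This rests on two monitor periods of equal length, on the first being completed before fitting, and on the available text being the full collection procedure. The consent form could narrow the gap by giving a reporting instruction, but would not by itself add a scheduled enquiry. The conclusion concerns completeness of the safety record and makes no claim about the walking results.

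**What to change.** - Add a short adverse-event item set to the take-home ASKp form at both visits: skin problem under either cuff, soreness, and days a monitor was off and why.
- Add an adverse-event entry to the baseline column of the schedule.
- Define the end of adverse-event collection as receipt of the second form.
- Have study staff pass any positive answer to the principal investigator on receipt, so that the stated ongoing review has a route.
- Reconcile the 7-day and two-week wear statements, and have the new items answered at the end of wear so that they cover the whole period.

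The cost is a schedule edit and about half a page on a form already in use. Families spend a few more minutes, and staff log a few more mild events. No extra visit is needed.
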